2.3 Applicable Standard Operating Procedures

The applicable Standard Operating Procedures (SOPs) of Assign DMB for this study are: STAT01 Statistical Analysis File STAT03 Statistical Analysis Plan STAT04 Interim Analysis STAT06 Data Review Meeting STAT07 Report Writing SAS01 SAS General Principles SAS04 Handling of Statistical Analyses

2.4 Blinding and Randomization

As it is an open-label and single arm study, principles of blinding and randomization are not applicable.

2.5 **Descriptive Analyses**

- Descriptive analyses of continuous variables (summary statistics) will be described with the number of nonmissing observations, arithmetic mean, standard deviation (±SD), median, quartiles (Q1 and Q3) and range (minimum and maximum).
- Categorical variables (frequency statistics) will be described with the number of non-missing observations and percentages (%).

2.6 Inferential Analyses

Inferential analysis for efficacy is described in Section 5.3. Inferential analysis for safety is described in Section 6.2.3.

2.7 Center and Country Effect

Since this study is a one-center pilot study, stratification by country or study site is not applicable.

2.8 Handling Missing Data

In general, missing data will not be imputed and analysis is restricted on available data, with the following exceptions:

- For time-to-event endpoints (DFS, OS), incomplete dates will be handled as described in Section 5.2.
- Response rates will consider missing response assessments as described in Section 5.2.
- Missing causality assessment for adverse events will lead to handling of the AE as related (see Section 7.3 . of the CSP)

2.9 **Protocol Deviations**

Potential protocol deviations will be collected prior to database snapshot for the main analysis. Potential protocol deviations will be discussed in a data review meeting (DRM) prior to database snapshot for the main analysis and will be classified as relevant or not relevant. A protocol deviation will be considered relevant if it has a potential influence on the efficacy analysis. Relevant protocol deviations will lead to exclusion from the PP Population. Relevant protocol deviations can be one of the following but are not limited to:

- at least one of the major inclusion criteria was not met (criteria with relevant impact on efficacy)
- at least one of the major exclusion criteria was fulfilled (criteria with relevant impact on efficacy) •
- administration of prohibited therapies during the screening and treatment phase as defined in the CSP •
- administration of no study treatment •
- no documentation of tumor assessment after start of study treatment •
- erroneous dose of study medication .

Medical Coding 2.10

All information regarding the medical coding of medical history and adverse events can be found in the coding guideline.

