1.3 Endpoints

- 1.3.1 Primary Endpoint
 - Frequency and severity of AEs including peri- and post-operative complications (grade 2-4 AEs according to NCI-CTCAE V4.03)
 - o number of patients treated in compliance with protocol
 - Tumor response evaluation

clinical response parameters:

- o response rates (Δ tumor size / lymph node size), according to RECIST 1.1 criteria
- Δ PET-activity (standardized uptake value [SUV]) (analysis of this end point is not covered in this SAP)
 Pathologic response parameters:
- Pathologic regression grading according to Junker criteria (see Appendix 3 of CSP)
- 1.3.2 Secondary Endpoints
 - disease free survival
 - overall survival

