1.5 Schedule of Study Assessments

| Study Phase | Screening | Treatment phase | | Pre- Surgery | Dis-charge | End of treatment | Follow-up |
|---|------------------|-------------------|-------------------|-----------------|------------|---------------------|-------------------|
| Visit | SCR | V1 | V2 | PS | D | EOT | FU1 – FUx |
| Time windows | Day - 28 to 0 | Day 1 | Day 21 +/- 3 days | Day 43-50 | Day 60-74 | 6 wks. after | every 3 months |
| Informed consent | X | | | | | Surgery | |
| Demographics | Х | | | | | | |
| (age, gender, race) | | | | | | | |
| Tumor diagnosis | Х | | | | | | |
| Cancer history | Х | | | | | | |
| Medical history (incl. smoking status) | Х | | | | | | |
| Previous treatments | X | | | | | | |
| Tumor assessments (PET)-CT, RECIST 1.1 | X | | | х | | | |
| Tumor staging | х | | | | | | |
| (PET-CT, MRI DIalit) Chest X ray | Y | | Y | × | × | Y | |
| Cardiac evaluation | ~ | | ^ | ^ | ^ | ^ | |
| (12-lead ECG) | × | | (X) ¹ | Х | | X | |
| Physical examination ² | Х | | X | Х | X | X | |
| Body weight and height / BSA ³ | X | | X | X | | X | |
| Vital signs | Y | 001 | v | × | V | × | |
| (BP, HR, body temperature) | ^ | (∧)° | ^ | ^ | ^ | ^ | |
| Lung function test | х | | x | x | | х | |
| ECOG status | Y | | ¥ | × | | × | |
| Pregnancy test (if applicable) | × | (X) ⁸ | ^ | ^ | | ^ | |
| Hematology4 | X | (X) ⁸ | X | X | X | × | |
| Coagulation | X | (X) ⁸ | X | X | X | X | |
| Clinical chemistry ⁵ | X | (X) ⁸ | X | X | X | X | |
| tumor marker | X | | | X | ~~~~ | X | |
| TSH ⁶ | X | | X | X | X | X | |
| In- / Exclusion criteria | X | | | | | | |
| Biomarkers (blood sample) | | X | Х | Х | X | Х | |
| Tumor tissue ⁹ | Х | | | | Х | | |
| HR-QoL | Х | | | Х | | Х | |
| Treatment (V1/V2) | | Pembrolizumab 200 | Pembrolizumab 200 | | | | |
| Concomitant medication | Х | | Contin | uously | | 1 | |
| Concomitant procedures | X | | Contin | uously | | | |
| Adverse events X | | Contin | uouslý | | | X7 | |
| Subsequent cancer therapy | | | | | | | Х |
| Survival status | | | | | | | Х |

¹ if clinically indicated. Consult a specialist if clinically abnormal and exclude any immune-related myocarditis.

² Full examination is required at baseline and end of treatment. Focused clinical examination shall prevail throughout the course of treatment.

³ Body height will only be measured at screening.

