5. EFFICACY ANALYSIS

Efficacy analyses will be performed primarily on the PP Population and will be repeated on the the ITT population.

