5.1 Data Points

Adapted from:

Following tables and figures will be provided:

- Tumor response at pre-surgery visit
 - o Overall response
 - \circ Δ tumor size
- Tumor regression grading stage (according to Junker criteria)
- Kaplan-Meier statistics for disease free survival (DFS)

Page 12 of 23

- Kaplan-Meier statistics for overall survival (OS)
- Tumor staging
- Tumor markers (CEA, Cyfra 21-1)
- Lung function
 - o forced expiratory pressure in 1 second (FEV1)
 - maximum vital capacity (VC MAX)
 - forced vital capacity (FVC)
 - inspiratory vital capacity (VC IN)
 - diffusion capacity of lung for CO (DLCO SB)
 - o diffusion capacity of lung for CO / alveolar volume (DLCO/VA)
 - o DLCOc SB
 - o DLCOc/VA
 - forced expiratory pressure in 1 second / maximum vital capacity (FEV1 % VC MAX)
 - partial pressure of 02 (p02)
 - partial pressure of CO2 (pCO2)

Corresponding details on the patient-level will be listed.

The following information will be provided only in data listings:

- Screening tumor assessment
- Target lesions
- Non-target lesions
- Translational research
- Survival status

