5.2 Definitions

- Disease-free survival (DFS) will be defined as the time length from the date of surgery to the date of tumor recurrence or death (tumor recurrence as reported on follow-up pages in the eCRF, death as reported in the end of study page in the eCRF). Patients that had no tumor recurrence and did not die will be censored at the date of last contact when patient was alive (as reported on the end of study page in the eCRF).
- Overall survival (OS) will be calculated as the time length from the date of surgery to the date of death. Patients that did not die will be censored at the date of last contact when patient was alive (as reported on the end of study page in the eCRF).
- For both DFS and OS the following rule will be applied for incomplete dates: The date of surgery is assumed to always be completely known (day, month and year available), otherwise DFS and OS will not be calculated. For the end dates (death, tumor recurrence, last date patient was alive) patients will be secured at the earliest possible date. E.g. if the date of death is "UK/05/2019" then the patient is censored at 01/05/2019 and thus being considered event-free until this date and status is considered unknown after

this date. If this rule results in negative survival time, the patient is not considered for Kaplan-Meier analysis.

• Δ tumor size will be defined as the difference [mm] between "current SUM LD" and "baseline sum LD" on the tumor response assessment page of the eCRF.

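### SAP 2.8 refers missing response assessments to a rule that SAP 5.2 does not contain, and the default then makes pathologic response conditional on resection and grading

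*SAP*

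**What the plan says.** SAP 2.8 sets a general default: "In general, missing data will not be imputed and analysis is restricted on available data". It then lists exceptions, one of which is "Response rates will consider missing response assessments as described in Section 5.2".

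SAP 5.2 defines DFS, OS, the handling of incomplete dates ("For both DFS and OS the following rule will be applied for incomplete dates") and the change in tumor size. It does not mention a missing or non-evaluable response, and it gives no denominator. SAP 5.1, 5.3 and 7.1.3 and protocol 8.4.3 do not supply one either.

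For categorical data SAP 2.5 says "Categorical variables (frequency statistics) will be described with the number of non-missing observations and percentages", without stating the percentage base.

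SAP 1.3.1 uses the term response rates for the RECIST component of the primary endpoint and lists the pathologic component separately: "Pathologic regression grading according to Junker criteria (see Appendix 3 of CSP".

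On populations, SAP 5 states: "Efficacy analyses will be performed primarily on the PP Population and will be repeated on the the ITT population". PP excludes patients with no tumor assessment after treatment start (SAP 2.9, protocol 8.3.2). ITT is everyone enrolled (SAP 2.11.1).

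**The concern.** RECIST response and regression grade are both components of the primary endpoint, and no efficacy test is planned. The reported proportion is therefore the result, and its denominator is part of its definition. The SAP's authors evidently meant to write a rule for missing responses, and it is not there.

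The documents themselves foresee missing assessments. The planned RECIST output is "Tumor response at pre-surgery visit", and the schedule row "Tumor assessments (PET)-CT, RECIST 1.1" is marked only at screening and pre-surgery. Under protocol 3.1, a patient with progression or intolerable toxicity during immunotherapy goes to the end-of-treatment visit and follow-up, where no RECIST assessment is scheduled. Listing 16.2.3.5 has a field for why grading was not done.

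Patients who fail early are thus among those most likely to lack an assessment. If they leave the denominator, the rate describes those who reached the scan or the operation rather than those who were treated.

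**Working it through.** **1. Which rule applies to whom**

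| Situation | ITT table | PP table |
|---|---|---|
| RECIST, no scan after treatment start | In the population; percentage base not stated | Excluded from PP |
| RECIST, scan not evaluable | Not stated | Not stated |
| RECIST, progression seen only on an unscheduled scan (protocol 5.1.1) | Not stated | Not stated; PP membership is settled at the data review meeting |
| Junker, not resected or not graded | Plain reading: non-missing default, so out of the denominator | Same; lack of grading is not a listed PP deviation, though the list is open-ended |

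For RECIST, the available-data default cannot fill the gap, because SAP 2.8 expressly takes response rates out of it.

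**2. The plan's own figures**

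Protocol Table 3 gives exact (Clopper-Pearson) 95% intervals at N=30. With x = 30p:

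- Pathologic response, p = 0.43: x = 12.9, interval 25.2–62.3. This matches the table.
- RECIST response, p = 0.10: x = 3, interval 2.1–26.5. This matches the table.

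With whole patients, the nearest count to 43% is 13/30 = 43.3% (25.5–62.6). Protocol 1.3 gives the source of the 43% as 9/21 of all treated subjects: 9/21 = 42.9%. Both the reference rate and the N=30 interval therefore use a denominator that is not restricted to resected and graded patients.

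**3. Size of the effect (illustration)**

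Let R be the responders and k the number of the 30 without an assessment. With R held fixed, dropping the k patients moves the rate from R/30 to R/(30−k). The shift in percentage points is 100·R·k / [30·(30−k)].

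The documents do not give k, so 0 to 6 is an assumption. The upper end, 6/30 = 20%, equals the non-resection proportion in the protocol 5.4 stopping rule (3/15). It is not a forecast.

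| k | Pathologic, R = 13 | Shift | RECIST, R = 3 | Shift |
|---|---|---|---|---|
| 0 | 13/30 = 43.3% (25.5–62.6) | 0 | 3/30 = 10.0% (2.1–26.5) | 0 |
| 1 | 13/29 = 44.8% (26.4–64.3) | 1.5 | 3/29 = 10.3% (2.2–27.4) | 0.3 |
| 2 | 13/28 = 46.4% (27.5–66.1) | 3.1 | 3/28 = 10.7% (2.3–28.2) | 0.7 |
| 4 | 13/26 = 50.0% (29.9–70.1) | 6.7 | 3/26 = 11.5% (2.4–30.2) | 1.5 |
| 6 | 13/24 = 54.2% (32.8–74.4) | 10.8 | 3/24 = 12.5% (2.7–32.4) | 2.5 |

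Check at k = 6: 100·13·6/(30·24) = 10.8, and 100·3·6/(30·24) = 2.5.

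These shifts come from the missing-assessment rule alone. The documents allow no figure for the effect of leading with PP.

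**The case against.** - **SAP 2.13 puts all patients of the population in the table column.** This favors an all-patient reading of the ITT table. But it is a layout rule and does not fix the base of the percentages, so the gap remains.
- **Junker grade already has a rule.** This largely stands. On the plain reading of SAP 1.3.1, the non-missing default governs grading. A reader might infer that Junker grade has no rule at all; the documents do not support that. Counting unresected patients as non-responders targets a different quantity. It is preferable here because it matches Table 3, not because the default is absent.
- **The 10.8-point figure overstates the problem.** This stands. It needs an assumed k = 6 and a combined IIb+III rate that SAP 7.1.3 does not list; Table 14.3.2 shows regression stages. At k of 1 or 2 the shift is 1.5 to 3.1 points, inside an interval about 37 points wide (62.6 − 25.5).
- **The RECIST effect lies mostly outside the lead table.** This also stands. PP already removes unscanned patients, and a patient found unresectable at the pre-surgery visit would lack a grade but still have the scan. The RECIST k may therefore be smaller than the Junker k.
- **Leading with PP is a legitimate choice.** The protocol names no lead efficacy population, so reading this as a contradiction would be wrong. It is still the weaker choice: PP removes patients without a post-treatment scan, and its membership is decided in a meeting, from an open-ended list, in an open-label trial.
- **A reader could rebuild the all-patient rate from the ITT listings.** True, but that does not prespecify the analysis.

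**Conclusion.** The point holds as a cheap improvement, minor to should-fix. The cross-reference from SAP 2.8 to 5.2 is broken. For RECIST this leaves the ITT percentage base unstated and, in PP, only non-evaluable and unscheduled-only scans open. For Junker grade the default makes the distribution conditional on resection and grading, so it cannot be set directly beside the 43% reference.

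In the illustration the pathologic rate moves from 43.3% to between 44.8% (k = 1) and 54.2% (k = 6), and the RECIST rate from 10.0% to 12.5% at most. This assumes 13 and 3 responders and an assumed number unassessed. With none missing there is no effect.

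A reader might go further and infer that the primary result is invalid or that a decision would change. The documents do not support that: SAP 5.3 plans no efficacy test, no response threshold is set, and neither power nor sample size depends on this rule. What changes is a descriptive estimate and how it can be compared.

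**What to change.** 1. In SAP 5.2, write the rule that 2.8 promises:
   - Patients with no evaluable pre-surgery RECIST assessment count as non-responders.
   - Progression documented on an unscheduled scan is reported as progressive disease, not as missing.
   - Patients not resected or not graded stay in the pathologic denominator as non-responders, shown in a separate row with reasons.
2. State that this rule, not the available-data default in SAP 2.5 and 2.8, governs Junker grade.
3. In SAP 5, lead RECIST response and Junker grade with the ITT tables already planned. SAP 2.11.3 merges ITT with Safety if everyone enrolled is dosed. If not, also show the all-treated rate for comparison with the 43% reference. Keep PP and assessed-only results as supportive.
4. Report grades IIb and III together as one rate with an exact 95% CI, to match Table 3.

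The cost is some SAP wording, a change in table order, one extra row and one extra rate. No new data are needed: the reasons for missing grading are already collected for Listing 16.2.3.5. The downside is that the headline response rate may be lower.

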2.11 Analysis Populations

2.11.1 Intent-to-Treat population

The Intent-to-Treat (ITT) Population includes all enrolled. A patient is regarded as enrolled if considered eligible for treatment start at screening (i.e. eCRF question "Have all screening assessments been performed and is patient considered eligible for treatment start" is answered with yes by the investigator).

2.11.2 Per-Protocol population

The Per-Protocol (PP) Population will comprise all patients of the ITT population who had no protocol deviation relevant for efficacy evaluation. PP Population will be defined in the DRM performed before the main analysis. For definition of relevant protocol deviations, see Section 2.9.

2.11.3 Safety population

The safety population consists of all patients who received at least one dose of study medication.

If the Safety and ITT Population are identical (i.e. all enrolled patients received at least one dose of treatment medication) the analysis will be performed for the Safety Population and the ITT Population together, labelled with "Safety/ITT Population".

2.12 Patient Data Listings

All recorded patient data of eligible patients will be included in by-patient data listings. Safety data listings will be restricted to the safety population (treated patients).

Data listings will include the patient number as identifier (and parameter and/or time point if available). A column indicating if a patient is in the PP Population will be shown in all baseline and efficacy listings.

2.13 Table Columns

All analysis tables will include one column including all patients of the respective analysis population.

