3.2 End of Treatment

End of Treatment is defined as 6 weeks post surgery (approx. 4 weeks post discharge). In patients who discontinue during the treatment phase, an End of Treatment (EOT) visit will be performed within 28 days after treatment discontinuation.

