7.5 Safety recording and reporting requirements

7.5.1 Recording periods

- Adverse events are recorded from time of signed informed consent until 6 weeks (EoT visit) after surgery.
- Serious adverse events are recorded from time of signed informed consent until 90 days after last dose of IMP or for 6 weeks after surgery if the subject initiated new anticancer therapy (e.g. radio-chemotherapy)
- Pregnancies occurring in a study subject are recorded from time of signed informed consent until 120 days after last dose of IMP.

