8.2 Sample Size Calculation

A phase II approach will be used to generate preliminary hypothesis generating data. No formal sample size estimation has been performed. The scope is to gather information on feasibility, safety and efficacy.

Target sample size is N=30

The rationale for the sample size of this trial is based on ethical, clinical as well as scientific considerations. The neo-adjuvant treatment approach with an immune check-point inhibitor is highly experimental with only limited data on safety and feasibility available. Therefore, only a small number of patients should be subjected to this experimental treatment. Nevertheless, the sample size should allow the generation of statistically meaningful evidence for feasibility and safety to permit the decision to further develop this treatment approach.

With a sample size of N=30 and assuming that the number of events follows a binomial distribution B(30,p), events with an incidence rate p > 9.5% will be observed at least once with a 95% probability. This observation limit will exclude individual pembrolizumab related SAEs but covers most of the historical reference events/rates of the primary endpoints in this trial as well as the early stopping rule.

The degree of the potential evidence provided by a sample size of N=30 is summarized in Table 3.

Table 3 Reported reference data and exact CI under a sample size of N=30 [Clopper Pearson
method] [13-15]

Adverse event / endpoint	Reported Frequency	95% CI for sample size of N=30
AE rate in Pembrolizumab monotherapy	97.4%	83.9 - 100.0
trials		
Drug related AE rate in Pembrolizumab	73.7%	54.5 - 88.0
monotherapy trials *		
SAE rate in Pembrolizumab monotherapy	37.2%	20.4 - 56.7
trials *		
Drug related SAE rate in Pembrolizumab	10 %	2.1 – 26.5
monotherapy trials *		
Cumulative rate of the 5 most frequent	9.4%	1.8 – 25.7
SAEs in Pembrolizumab monotherapy		
trials and potential impact on neo-adjuvant		
treatment approach and/or surgery		
[pneumonia (3.0%), pleural effusion		
(1.7%), pneumonitis (1.6%), dyspnea		
(1.6%) and pulmonary embolism (1.5%)] *		
number of patients treated in compliance	80 %	61.4 – 92.3
with protocol / Feasibility of resection and		
early stopping rule [#]		
Radiologic response (CR or PR) per	10 %	2.1 – 26.5
RECIST 1.1 §		
Pathologic response (grade IIb or higher as	43 %	25.2 - 62.3
per Junker criteria) [§]		
* See also section 1.2.4 and IB of pembrolizur	nab	1

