6.2.1 Data Points

- Adverse Event Overview
 - o Any AE
 - Any AE of clinical interest
 - o Any related AE
 - o Any severe AE
 - Any AE grade 2-4
 - Any related severe AE
 - o Any related AE grade 2-4
 - o Any SAE
 - Any related SAE
 - Any AE requiring study treatment dose modification
 - o Any AE requiring study treatment discontinuation
- Adverse Events by maximum severity
 - o Any AE
 - o Any related AE
- Adverse Event by highest relationship
 - o Any AE
 - o Any AE grade 2-4

Adapted from:

STAT03_A Statistical Analysis Plan Version 6.0, Effective Date 16-Feb-2018

Confidential and intellectual property of Assign DMB. No part of this document or its contents may be duplicated, referenced, published or otherwise disclosed in any form or by any means without prior written consent of Assign DMB.

- o Any SAE
- Adverse Events by SOC and preferred term
 - o Any AE
 - Any related AE
 - Any AE grade 2-4
 - o Any related AE grade 2-4
 - Any SAE
 - Any related SAE
 - Any AE requiring study treatment discontinuation
- 6.2.2 Definition
 - Severe AE: AEs with severities of Grade 3-5 (severe or medically significant, severe or life threatening, death) will be considered as severe AEs
 - Missing causality assessment for adverse events will lead to handling of the AE as "related", see Section 7.3 of the CSP.

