| 16.2.4.16 | Surgeries performed (Safety Population) | Patient ID, Surgery performed, Date of surgery, |
| | | Method, Approach, Extensions, Systematic lymph |
| | | node dissection performed, Intraoperative blood |
| | | loss [m]], Intraoperative blood transfusion |

| | | performed, Post-operative complications, Length |
|-----------|---|---|
| | | of ICU stay, Re-admission to ICU, Date of re- |
| | | admisson |
| 16.2.4.17 | Vital signs (Safety Population) | Patient ID, Visit, Parameter, Value, Unit |
| 16.2.4.18 | Cardiac evaluation (Safety Population) | Patient ID, Visit, Evaluation performed, Cardiac |
| | | evaluation, Date, Result, Specification of |
| | | abnormality |
| 16.2.4.19 | ECOG performance status (Safety Population) | Patient ID, Visit, Date ECOG Score, ECOG Score |
| 16.2.4.20 | Routine Chest X-Ray (Safety Population) | Patient ID, Visit, Chest X-Ray performed, Date of |
| | | performance, Tumor visible, Comments |
| 16.2.4.21 | Pregnancy test (Safety Population) | Patient ID, Visit, Pregnancy test performed, Date |
| | | of test, Reason not performed, Method, Result |
| 16.2.4.22 | Quality of Life (Safety Population) | Patient ID, Visit, Date of assessment, Quality of |
| | | Life question, Answer/Result |

Page 23 of 23

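### AE tables are not split at surgery, and no planned table gives the complication rate in operated patients, although the primary endpoint names these complications

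*SAP*

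**What the plan says.** - **Endpoint.** SAP 1.3.1, like protocol 2.4, lists among the primary endpoints "Frequency and severity of AEs including peri- and post-operative complications", expressed as CTCAE grade 2 to 4 events. Protocol 1.4 names the lack of perioperative safety knowledge as a risk and makes closing that gap a goal of the pilot.
- **Window.** Protocol 7.5.1: "Adverse events are recorded from time of signed informed consent until 6 weeks (EoT visit) after surgery". The discharge and EOT visits (protocol 5.2.4 and 5.2.5) collect peri-operative complications together with AEs.
- **Tables.** SAP 6.2.1 and 7.1.4 plan Tables 14.4.1 to 14.4.4: an overview, then maximum severity, highest relationship, and SOC and preferred term. They include drug-related rows such as "Any related AE grade 2-4". None is divided by period. All use the Safety Population, which is every patient given at least one dose (SAP 2.11.3), and AE rates carry 95% Wilson intervals (SAP 6.2.3).
- **Surgery output.** SAP 7.1.4 has no surgical table. The dedicated field is in Listing 16.2.4.16, whose contents read in part "performed, Post-operative complications, Length".
- **Causality.** Protocol 7.3 offers related or not related, to study drug only. SAP 2.8 counts a missing assessment as related.
- **Layout.** SAP 2.13: "All analysis tables will include one column including all patients of the respective analysis population".

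**The concern.** The trial asks two safety questions: are two doses before surgery tolerated, and is the operation afterwards safe? Lung resection produces AEs of its own. An all-cause rate running across both periods cannot show which one the events came from. It also puts surgical events over a denominator that includes patients who never had surgery. At stake is whether a named component of the primary endpoint is reported as a rate at all, or has to be rebuilt by hand from listings.

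**Working it through.** **1. The plan's own figure.** Protocol 8.2 and SAP 1.4 say that with N=30 an event with incidence above 9.5% is seen at least once with 95% probability. Check: 1 − 0.05^(1/30) = 9.50%, and 1 − (1 − 0.095)^30 = 0.9499. The figure reproduces.

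**2. How much of the window is post-operative.** Protocol 3.2 puts EOT six weeks after surgery and about four weeks after discharge, so surgery falls about two weeks before discharge. Discharge is at Day 60 to 74 (schedule of assessments), so surgery is at about Day 46 to 60, which is 45 to 59 days after Day 1. The post-operative part is 42 days. Its share of the time from first dose to EOT is 42/(59 + 42) = 42% to 42/(45 + 42) = 48%. Neither period is negligible.

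**3. What the all-cause row can distinguish.** Let a be the proportion with an event before surgery, b the proportion of operated patients with one after it, and s the proportion operated. Assuming independence, the pooled rate is 1 − (1 − a)(1 − s·b). The values of a and b are assumed.

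| a | b | s | Pooled rate |
|---|---|---|---|
| 10% | 50% | 1 | 1 − 0.9 × 0.5 = 55% |
| 50% | 10% | 1 | 1 − 0.5 × 0.9 = 55% |
| 10% | 50% | 0.8 | 1 − 0.9 × 0.6 = 46% |
| 50% | 10% | 0.8 | 1 − 0.5 × 0.92 = 54% |

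Opposite safety profiles give the same row when all patients are operated. At 80% operated they differ by 8 points. For scale, a 95% Wilson interval at N=30 around 43% runs from 27.1% to 60.5%.

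**4. The denominator.** The documents do not give the number operated. I use 24 as an example, which is 80% of 30, the feasibility level in protocol 8.1. Suppose 8 patients have a post-operative complication (assumed). The Wilson interval is [p + z²/2n ± z√(p(1−p)/n + z²/4n²)] / (1 + z²/n) with z = 1.96.

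- Safety Population: 8/30 = 26.7% (14.2% to 44.4%).
- Operated patients: 8/24 = 33.3% (18.0% to 53.3%).

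The first rate equals the second multiplied by 24/30.

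**5. What the right denominator costs in precision.** The limit in step 1, 1 − 0.05^(1/n), is 9.5% for n=30, 10.5% for n=27, 11.7% for n=24 and 13.9% for n=20.

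**6. Can the split be made?** Yes. Listing 16.2.4.2 holds AE start date, grade and causality, and Listing 16.2.4.16 holds the date of surgery.

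**The case against.** The case against is substantial, and much of it stands.

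- **Drug safety is not unreadable.** A reader might infer that the tables show neither drug nor surgical safety. The documents do not support that. Related AEs, related severe AEs, related grade 2 to 4 AEs and related SAEs all have planned rows, and Table 14.4.3 goes by highest relationship. Their limits are an open-label binary judgement and missing causality counted as related. They also offer no attribution to surgery, so the unrelated remainder mixes surgical, tumour and background events.
- **Complications are not confined to a listing.** Those recorded as AEs enter the grade 2 to 4 rows and the SOC and preferred-term tables, but cannot be identified there. Only the dedicated field is listing-only.
- **SAP 2.13 does not prescribe pooling over time.** One patient column is natural in a single-arm trial, and under the same rule the laboratory tables are shown by time point.
- **Protocol Table 3 does not show harm from pooling.** Besides the all-cause row "SAE rate in Pembrolizumab monotherapy" (37.2%), it has drug-related rows (AE 73.7%, SAE 10%) that the planned related rows match. No test or decision rule against Table 3 is planned. A reader might add an assumed surgical SAE rate to 37.2% and see the total pass the upper limit of 56.7%. That needs a surgical rate above 1 − 0.433/0.628 = 31%, and the documents give no surgical SAE rate.
- **Comparing only pre-surgery AEs with Table 3 would be wrong too.** Protocol 6.3.1 expects that immune events may appear months after the last dose, so this would truncate drug toxicity.
- **The listings allow reconstruction.** True, but reconstruction by hand does not replace a planned summary of a primary endpoint component.

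**Conclusion.** The point holds in limited form. Followed as written, the SAP yields all-cause AE rates that cannot separate pre-surgical from post-surgical risk, and no rate of peri- or post-operative complications in operated patients. The related-AE rows cover the drug side by investigator judgement; nothing planned covers the all-cause post-operative side. That judgement cannot stand in for it, because whether prior pembrolizumab affects surgical outcome is part of what the pilot is meant to learn.

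The size depends on numbers the documents do not give. With 24 of 30 operated, a surgical rate is understated by a factor of 0.8 (26.7% against 33.3% in the example); with all 30 operated there is no dilution and only the mixing of periods remains. The 55% example rests on assumed rates and independence. This is a worthwhile and cheap improvement to the reporting. It does not invalidate the safety analysis, and it does not show that the pooled rates will exceed any reference limit.

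**What to change.** 1. In Tables 14.4.1, 14.4.2 and 14.4.4, show three columns: *first dose to before surgery*, *surgery to EOT* with operated patients as denominator, and *overall* as now planned. Assign events by AE start date against date of surgery, and amend SAP 2.13 to allow this. State where events on the day of surgery go, where the first column closes for patients never operated, and that AEs before the first dose and any SAEs recorded after EOT count in *overall* only.
2. Add one table of peri- and post-operative complications by maximum CTCAE grade in operated patients, with 95% Wilson intervals. Say how the field in Listing 16.2.4.16 is reconciled with complications recorded as AEs, so that none is missed or counted twice.
3. Keep the overall and related rows beside the period columns, and do not limit any comparison with protocol Table 3 to the pre-surgery column. A period split describes timing; it does not attribute cause.

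Cost: a few columns and one table, with no new data, patients or tests. The downside is wider intervals in the smaller operated group, as in steps 4 and 5 of the working.
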